2.4 Studies Planned in the Proposed Trial

Evaluation of anti-MUC1 antibody titer and MUC1 expression in adenomas in relation to adenoma recurrence

Anti-MUC1 IgG will be measured at w12 and w55 to measure the immune response to the vaccine in comparison to placebo, and at the time of the endpoint surveillance colonoscopy to examine the relationship between antibody titer and adenoma recurrence. In addition, sections of the qualifying advanced adenoma and of any recurrent adenomas will be obtained. Comparison of tumor associated

MUC1 antigen expression on the recurrent adenomas in relation to antibody response, and comparison among vaccine responders, non-responders, and the control group are planned.

Evaluation of anti-MUC1 antibody responses and pre-vaccination levels of circulating MDSC

Heparinized blood will be collected at week 0, 2, 10, and 12 and live PBMCs stored in DMSO and LN2 at -70 to -80°C. We plan measurements of levels of circulating MDSC in all participants. We know from the feasibility study that higher levels of MDSC were associated with lack of generation of vaccine induced antibodies. We will confirm this observation in a larger number of individuals and will evaluate MDSC levels as a variable influencing adenoma recurrence. In the placebo group, we expect to have MDSC low and MDSC high individuals in whom we can determine if adenoma recurrence rates might correlate with MDSC.

Using samples stored in the biorepository, eventually, stored PBMCs will be used to evaluate MUC1 specific T helper and CTL responses. These studies are more time intensive and expensive and funding for them will have to be obtained through other sources or other NCI grants. We do not anticipate difficulty obtaining funding for sophisticated immune assessments on this unique collection of clinical samples among participants undergoing a randomized trial of immunotherapy in a prevention setting. Within this trial, we are using T dependent antibody responses and T dependent memory responses as a surrogate marker of vaccine elicited T cells.

Placebo Response

There are several important reasons to include a placebo group. We do not know the frequency of spontaneous acquisition of antibodies to MUC1, nor do we have data on the natural history of fluctuation in antibody level over time. A control group with which to compare the antibody response and a control group with which to compare adenoma recurrence is essential.

Exclusion of Individuals with Cancer

We are intentionally not enrolling participants with cancer (within the previous 5 years), even early stage cancer. By the time a cancer is present, the immune system has been exposed to and has attempted to cope with the lesion for some time. Attesting to the value of an intact immune system, the antibody response rates observed in our preliminary study far exceed that observed in previous trials of participants with cancer. Even in the setting of advanced adenoma, the pilot study showed signs of immunosuppression (higher levels of MDSC) in some patients. All cancer patients have elevated levels of these and other immunosuppressive cell populations.

How does the proposed trial differ from the completed feasibility study?

The completed study was performed to assess immune response, evaluate toxicity, and to trial recruitment, consent, and vaccine administration. The completed study was a resounding success in terms of enrollment, follow up, absence of adverse events, and immune response. The eligibility criteria included a history of advanced adenoma that could have been diagnosed years prior. The mean time from advanced adenoma diagnosis to vaccination in included participants was 824 days with a range up to 3500 days. As such, participants had interim colonoscopy exams prior to vaccination, and assessment of the effect of vaccine on adenoma recurrence is not possible. A significant difference in the proposed trial is the synchronization of vaccine administration with diagnosis of advanced adenoma such that a meaningful assessment of the vaccine on adenoma recurrence is attainable. A clinical endpoint is needed to advance immunotherapy in the prevention setting.

Laboratory Biomarkers

The most appropriate biomarker of vaccine efficacy is the immune response. We will measure the major T cell dependent anti-MUC1 antibody IgG isotype which requires MUC1 specific T cells to promote isotype switching by B cells from IgM. We will largely focus on anti IgG to MUC1, as that antibody isotype is easier to measure and more reproducibly induced. We will also measure MDSC levels to evaluate the relationship between MDSC and vaccine response. The biospecimen repository archive will include plasma and PBMC for immunologic and other assays, such as the frequency and quality of antigen-specific T cells induced by the vaccine or adenoma recurrence and changes in the serum cytokine and chemokine profiles. The tissue sections of adenomas will be also be useful in exploring the underlying hypothesis that vaccination can impair MUC1 expression and adenoma progression.

Conclusions and Implications

The robust antibody response obtained in our pilot trial in participants with a premalignant advanced adenoma challenges the assumption that tumor-associated antigens like MUC1 are subject to immune tolerance. Our data indicate that tumor or treatment-induced immune suppression was more likely responsible for ineffective immunization in cancer patients. The high level of antibody response in participants with pre-malignant disease attests to the promise of immunotherapy against tumor antigens as a means of prevention. Lack of toxicity will allow application of the vaccine in healthy as well as younger individuals with strong immune systems.

The proposed trial will add substantively to the pilot trial, because it offers **synchronization** of diagnosis and vaccine administration, and allows assessment of a clinical endpoint, adenoma recurrence. As the first randomized trial of immunoprevention, the trial offers a pioneering, innovative opportunity in cancer prevention research. The development of a biorepository will facilitate ancillary biomarker studies in this unique cohort and promise multiple opportunities for collaboration in and outside the NIH to make the trial even more productive over time.

3. SUMMARY OF STUDY PLAN

3.1 Study Parts

There are 3 Parts planned. Each Part will provide salient data on MUC1 immunoprevention, with continuation through Part III providing insight on the clinical efficacy of the vaccine.

1. Part 1 will include participant follow up to week 12 and will permit assessment of MUC1 vaccine response compared to placebo.
2. Part 2 will include participant follow up to week 56 and will permit assessment of MUC1 immune memory response to a booster dose of vaccine compared to placebo.
3. Part 3 will include participant follow up to week 156 and will permit assessment of the clinical endpoint of adenoma recurrence in participants with vaccine compared to placebo. Assessment of MUC1 expression on recurrent adenomas will allow assessment of whether vaccination can impair MUC1 expression and adenoma progression.

The vaccine is manufactured at the FDA certified peptide facility of the University of Pittsburgh. The vaccine will consist of 100 micrograms (0.1mg) of MUC1 100mer peptide dissolved in 50 microliters (0.05mL) of sterile saline, admixed with 500 micrograms (0.5mg) of the adjuvant poly-ICLC (Hiltonol®) in 250 microliters (0.25mL) volume, for a total injection volume of 300 microliters (0.3mL). Poly-ICLC is a

TLR3 agonist, a synthetic, non-replicating dsRNA with no specific genetic message, which acts as a viral-mimic and activator of diverse elements of both the innate immune response and of adaptive immunity. Participants randomized to placebo will receive an identically appearing injection of sterile saline.

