Other than viral vaccines for cancers of known viral origin, vaccines for prevention of cancer have not received sufficient attention. Yet, there are many non-viral antigens that are differentially expressed between normal and cancer cells, such as MUC1, that are perceived by the immune system as foreign and to which immune responses can be safely generated through vaccination. In preclinical animal models of human cancer, these vaccine-elicited immune responses have prevented cancer development or cancer progression. These studies have served as the basis for the first clinical feasibility study of the MUC1 peptide vaccine in individuals with the history of advanced adenoma who are considered at increased risk for developing colon cancer³⁴. This study showed that the vaccine consisting of 100mcg of the synthetic 100mer MUC1 peptide admixed with the TLR-3 agonist Hiltonol as adjuvant, induced anti-MUC1 IgG and long term immune memory thus confirming its immunogenicity. The study also showed that individuals with above normal numbers of circulating myeloid derived suppressor cells (MDSC) were prevented from responding to the vaccine. The randomized placebo-controlled trial described in this protocol will confirm the vaccine immunogenicity and its dependence on the MDSC and compare adenoma recurrence in vaccine responders vs. non-responders.

Colorectal Adenomas

MUC1 is overexpressed and hypoglycosylated on premalignant lesions such as adenomatous polyps, and its expression is significantly greater with higher degrees of dysplasia⁷. MUC1 is functionally important in the maintenance of the malignant phenotype. Thus, induction of an immune response against MUC1 in the setting of pre-malignancy, such as in patients with adenomatous polyps, may protect from polyp recurrence as well as from progression to cancer.

[figure not shown]

Figure1: Abnormal MUC1 is overexpressed and hypoglycosylated. Hypoglycosylated MUC1 exposes the disaccharide T antigen and the shorter monosaccharide Tn antigen attached to the protein backbone of MUC1 molecules.

Mouse model of MUC1 vaccine for colon cancer prevention

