2.1 Study Disease: Advanced Adenomas

Advanced adenomas (AAs) are defined as pre-neoplastic adenomatous polyps that are either: 1) ≥ 1 cm in size, 2) demonstrate villous or tubulovillous histology, or 3) have severe or high grade dysplasia. Advanced adenomas occur in about 5-10% of patients undergoing screening colonoscopy. Individuals with AAs are a high risk group. Studies show that individuals having an advanced adenoma have a 2 fold or more risk of having a recurrent AA compared to individuals with non-advanced adenomas^{38,39}, and more importantly, are at higher risk for subsequent colorectal cancer, even years later^{8,40}. Patients with AA are an appropriate group to focus on for prevention. Low levels of anti-MUC1 IgG can be detected in patients with advanced adenomas⁴¹. Most recently, we performed a pilot study of MUC1 vaccine in patients with a prior history of advanced adenoma, though not necessarily recently diagnosed advanced adenomas, and the vaccine was well tolerated with no significant toxicity³⁴.

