10.2.3 Tissue Specimens

Paraffin blocks and/or unstained slides from the polyps/adenomas removed during routine colonoscopy, pre- and post-intervention, will be requested from the institution at which the procedure was performed.

Tissue paraffin sections will be deparaffinized by baking overnight at 59°C. Endogenous peroxidase activity will be eliminated by treatment with 30% H₂O₂ for 15 min at room temperature. Antigen retrieval will be performed by microwave heating in 0.1% citrate buffer. Nonspecific binding sites will be blocked with Protein Blocking Agent (Thermo-Shandon Corp). Sections will be immunostained with anti-MUC1 antibody HMPV, which recognizes all forms of MUC1 by binding the epitope APDTR in the VNTR region in a glycosylation-independent manner (BD Pharmingen) and anti-MUC1 antibody VU-4H5 (Santa Cruz Biotechnology), which recognizes the epitope APDTRPAP in the VNTR region of hypoglycosylated MUC1 (Santa Cruz Biotechnology). Staining will be performed by the avidin-biotin peroxidase complex (ABC) method with a commercial kit (Vectastain ABC kit, Vector Laboratories). Color development will be performed by 3,3'-Diaminobenzidine (DAB) kit (BD Pharmingen).

Institutions that are unable to submit paraffin blocks may send five 5-micron unstained slides from each advanced adenoma as an alternative. Paraffin blocks and/or slides must be labeled with the participant ID number, specimen type, specimen number, and date of collection. Every effort must be made to make certain the specimen number on the block and/or slide labels corresponds to the polyp or adenoma number reported on the Colonoscopy Report CRF.

Send blocks/slides to:

CPN PC Office (Study MAY2013-01-01)
[name]
[name]

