13.10 Ancillary Studies

We will assess the following translational endpoints for this study.

- To compare the anti-MUC1 antibody titer at the time of surveillance colonoscopy to evaluate the anti-MUC1 antibody response in relation to adenoma recurrence. Since surveillance colonoscopy is generally at 3 years after an advanced adenoma, this titer will typically be obtained at approximately week 156.
- To evaluate MUC1 expression on baseline advanced adenomas and on recurrent adenomas detected at surveillance colonoscopy. Based on current knowledge of MUC1 expression and function in tumor cells, MUC1 negative adenomas are not expected to grow as immune escape variants, but this has never been tested before and the trial will provide an appropriate setting to study this issue.
- To evaluate levels of circulating myeloid derived suppressor cells (MDSC) in the vaccinated and the placebo group and correlate with anti-MUC1 antibody levels and adenoma recurrence.
- To establish a biospecimen repository archive including live cells, plasma, and germline DNA for future immunologic and other assays, for testing not currently accommodated within the budget of this trial.

Analysis of these translational endpoints:

Laboratory measures will be correlated with participant outcome (i.e., adverse events, IgG levels, etc.) and with each other as well. Cut-points will be determined based on previously defined and accepted standards. Descriptive statistics and simple scatter plots will be generated to review the continuous biomarker data. In addition, for continuous biomarker values, the actual and % change in the level of each of the biomarkers from baseline to post-baseline time points will be explored within each arm using Wilcoxon signed rank tests, and paired sample t-tests. Comparisons between MUC1 and placebo will be performed using a two-sample t-test or Wilcoxon rank sum test, as appropriate. All categorical variables will be analyzed using chi-square tests or Fisher's exact test. For all translational endpoints, any notable statistical result will be viewed as an impetus for further study rather than as a definitive finding in and of itself.

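### MUC1 expression can be measured only in participants who recur, so the planned tissue comparison cannot be read as a vaccine effect on expression without untestable assumptions

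*Combined protocol and SAP*

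**What the plan says.** Section 3.1 (Part 3) states the aim flatly: "Assessment of MUC1 expression on recurrent adenomas will allow assessment of whether vaccination can impair MUC1 expression and adenoma progression". Section 2.4 gives the contrast: comparison of "MUC1 antigen expression on the recurrent adenomas in relation to antibody response, and comparison among vaccine responders, non-responders, and the control group are planned". Section 13.10 lists the endpoint as "To evaluate MUC1 expression on baseline advanced adenomas and on recurrent adenomas detected at surveillance colonoscopy".

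Section 13.10 then has one general paragraph for all translational measures. For continuous biomarkers, "the actual and % change in the level of each of the biomarkers from baseline to post-baseline time points will be explored within each arm", by signed-rank and paired t tests. Vaccine and placebo are compared by t or rank-sum test, and categorical variables by chi-square or Fisher's test. Nothing is said about recurrence-free participants, several adenomas in one participant, or adjustment for size, histology or dysplasia.

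The qualifying lesion is advanced by definition (2.1, 4.1.1.1), whereas the recurrence endpoint counts any adenoma (1.2, 13.5). Section 2 says of MUC1 in premalignant lesions that "its expression is significantly greater with higher degrees of dysplasia".

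On tissue, 10.1 collects slides from the qualifying adenoma and from adenomas found at surveillance. Section 10.2.3 opens just as broadly, but its fallback says that sites unable to send blocks "may send five 5-micron unstained slides from each advanced adenoma as an alternative".

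**The concern.** Restricting the analysis to recurrent adenomas conditions on an outcome that the vaccine is designed to change. The vaccine is directed at MUC1, so selective prevention of MUC1-positive lesions is what success might look like. That leaves a higher share of MUC1-negative lesions among the recurrences that remain. Down-regulation within lesions, or outgrowth of escape variants (the possibility raised in 1.3), would leave the same trace. The responder/non-responder/control comparison adds a second grouping formed after randomisation. By the protocol's own account (2.3, 2.4), response is linked to suppressor-cell levels, which are themselves to be studied as an influence on recurrence.

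At stake is the interpretation of one translational question, together with a possible gap in the tissue that would be hard to fill later.

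**Working it through.** **1. The plan's figures.** Section 13.5 gives 45 evaluable participants per arm for Part III, one-sided alpha 0.05. It gives no sample size or power for the tissue analysis. The recurrence power does reproduce, with power = Φ{[(p1 − p2) − 1.645·√(2p̄(1 − p̄)/n)] / √[(p1(1 − p1) + p2(1 − p2))/n]}. For 50 vs 25%: (0.25 − 1.645 × 0.1021)/0.0986 = 0.833, so 79.8% (stated 79%). The other rows give 82.1% and 85.4% (stated 82% and 85%). The recurrence rates below are these design rates.

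**2. Participants with a lesion to stain.** 45 × 0.50 = 22.5 against 45 × 0.25 = 11.25. The other scenarios give about 20 vs 9 and 18 vs 7. Section 13.5 expects about 40% responders; if response were unrelated to recurrence, that is 0.40 × 11.25 = 4.5 vaccine responders with a lesion.

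**3. Selection with no change in any lesion.** MUC1 positivity is not in the documents, so it is assumed. Let P and N be the placebo probabilities of MUC1-positive and MUC1-negative recurrence, and let the vaccine prevent a fraction e of the positive ones only. The positive share among vaccine recurrences is P(1 − e)/[P(1 − e) + N].

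- With 50% recurrence, 80% positive: P = 0.40, N = 0.10, placebo share 80%.
- e = 0.5: 0.20/0.30 = 67%.
- e = 0.8: 0.08/0.18 = 44%.

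At the plan's 50 vs 25%, varying the assumed placebo positivity:

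| Placebo share positive | Vaccine share, all prevented lesions positive | Vaccine share, positives prevented twice as often as negatives |
|---|---|---|
| 50% | 0% | 33% |
| 70% | 40% | 58% |
| 90% | 80% | 85% |

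If prevention is unrelated to MUC1 status the share does not move. The distortion comes from selective prevention, not from fewer recurrences alone.

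**4. What the data can pin down.** Take 70% placebo positivity and assume that the vaccine never causes a recurrence. Among those who would recur in either arm (25% of participants), positivity under placebo can be as low as (0.35 − 0.25)/0.25 = 40% or as high as 100%, reached if all 0.15 of negative recurrences are among those prevented. The comparator needed for an effect on expression is only bounded.

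**5. Change from baseline, if that paragraph is applied to tissue.** Let h and l be positivity in advanced and non-advanced lesions, and a the advanced share of recurrences. With no vaccine effect the fall is (1 − a)(h − l). Assuming h = 80%, l = 30 to 50% and a = 10 to 40%, it runs from 0.6 × 0.30 = 18 points to 0.9 × 0.50 = 45 points. With h from 60 to 90% the range is 6 to 54 points.

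**6. A contrast in all evaluable participants.** In the e = 0.5 example, MUC1-positive recurrence is 40% vs 20% and MUC1-negative 10% vs 10%. This keeps the randomised groups, but it does not reveal the mechanism. Suppose instead that the vaccine prevents 40% of all lesions regardless of MUC1 (40 to 24, 10 to 6) and then turns one sixth of the remaining positives negative (4 points). The result is again 20% and 10%, now with real down-regulation.

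**7. Precision at 45 per arm.** Power for 40 vs 20%, by the formula in step 1, is Φ[(0.20 − 1.645 × 0.0966)/0.0943] = about 67%. For 10 vs 10%, the 95% interval is ±1.96·√(2 × 0.10 × 0.90/45) = about ±12 points. Among recurrences only (22 vs 11), two-sided power for 70 vs 40% positive is about 38%.

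**The case against.** The strongest reply is that the plan already treats this as exploratory. Section 13.10 regards any notable translational result as a reason for more work, not as a finding, and 2.4 speaks of exploring the hypothesis. That settles how much the point weighs. It does not remove the bias, and the sentence in 3.1 carries no such caution.

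Second, a comparison with placebo is planned in 2.4 and 13.10. Lesion grade should largely cancel between arms unless the vaccine changes the grade mix of recurrences. This stands: the grade problem belongs mainly to change from baseline. The selection problem does not cancel.

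Third, a reader might infer that a paired test of tissue expression is specified. It is not. The paragraph is generic, the listed measures include titer and suppressor cells, for which serial change is natural, and no change score between two different lesions is defined. Nor need every baseline lesion be highly dysplastic, since size or villous histology alone qualifies.

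Fourth, a reader might infer from 10.2.3 that slides of non-advanced recurrences will be lost. Section 10.1 and the opening of 10.2.3 both ask for them. Only the fallback sentence is narrower, so this is a mismatch to reconcile, not an established loss.

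**Conclusion.** The point holds as one of interpretation. Under the protocol's own hypothesis that the vaccine reduces recurrence, expression among recurrences is compared between groups selected by the outcome, and a lower positive share is not evidence of impaired expression. The size is illustrative: 80% to 67% if half of the positive lesions are prevented, 80% to 44% if four fifths are, and anything from no shift to a very large one across the assumptions shown.

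Two stronger readings are not supported. One is that the tissue data can show nothing: if the vaccine changed neither who recurs nor with which lesions, vaccine against placebo among recurrences would be a fair comparison, though the data cannot verify that condition. The other is that tabulating positive and negative recurrence in everyone identifies the mechanism; step 6 shows that it does not. It gives valid net effects of assignment.

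The consequence is confined to a translational endpoint. The primary analysis (13.4), the key secondary endpoints (13.5) and the decisions to proceed (13.9) are untouched.

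**What to change.** - **13.10:** make the main between-arm tissue analysis the proportion of all evaluable participants, recurrence-free included, with at least one MUC1-positive recurrent adenoma and, separately, with at least one MUC1-negative one. The two can overlap in a participant with several adenomas. Fix the positivity rule beforehand, for each of the two stains in 10.2.3, and report recurrences without stainable tissue as their own category. State that these are randomised net effects that do not separate prevention from down-regulation, and that precision is low at about 45 per arm.
- **13.10 and 2.4:** label expression among recurrent lesions, the responder comparison and any baseline-to-recurrence change as descriptive. Adjust for size, histology and dysplasia where numbers allow, and account for several lesions per participant.
- **3.1:** reword the sentence to match.
- **10.2.3:** let the slide fallback cover each qualifying and each recurrent adenoma, in agreement with 10.1. This is best done before surveillance tissue is collected.

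The cost is a little more analysis and a more modest claim. No tissue is needed beyond what 10.1 already requests.
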